8.0 Data and Specimen Banking For Future Undetermined Research

N/A

8.1 Data and/or specimens being stored

8.2 Location of storage

Duration of storage

8.3 Access to data and/or specimens

8.4 Procedures to release data or specimens

8.5 Process for returning results

9.0 Statistical Plan (Phase A)

9.1 Sample size determination

Statistical Plan & Sample size determination

Power Calculation: Our plan is to recruit 10 patients with Bulimia nervosa and PTSD in this trial. Here we show our power calculations for the Hypothesis 1 and 2 based on our best knowledge. It should be noted that we assume no carry-over therapeutic effect in the calculation (see **Study Design**).

We choose the CAPS distressing dream item as the primary measure of nightmare frequency. Based on previous studies in similar patient populations, we assume the baseline nightmare score equals to 6.5, regardless of the treatment period. We anticipate the mean (SD) nightmare score of 6.0 (1.5) after being administered placebo for 3 weeks, and the endpoint mean (SD) for after be treated with Prazosin would reduce to 3.5 (2.5). We assumed that the correlation between two scores for the same patient equals to 0.3. With a sample size of 10 patients, we will have 80% power to detect the treatment effect, at 2-sided alpha level of 0.05. Other scenarios are presented in the table below.

CAPS Nightmare score			Correlation coefficient	Power
Baseline	Placebo	Prazosin		
6.5	6.0 (1.5)	3.5 (2.5)	0.3	80%
6.5	6.0 (1.5)	3.5 (2.5)	0.4	85%
6.5	6.5 (1.5)	3.5 (2.5)	0.3	92%
6.5	6.5 (1.5)	3.5 (2.5)	0.4	95%
6.5	6.5 (1.5)	4.0 (2.5)	0.3	81%
6.5	6.5 (1.5)	4.0 (2.5)	0.4	85%

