1.0 Objectives

1.1 Study Objectives

The aim of our study is to evaluate the effectiveness of prazosin in bulimic patients experiencing distressing nightmares secondary to PTSD. We will be testing 10 participants. 8 will be tested using subjective measures (Phase A). If a signal of efficacy is detected the last 2 participants will be tested using additional objective PSG measurements (Phase B). Phase B will be a feasibility study and based on results PI will apply for external funding.

AIMS FOR PHASE A:

The Primary aim of our study is to evaluate the effectiveness of prazosin in bulimic patients experiencing distressing nightmares secondary to PTSD using subjective measures.

Hypothesis 1:

Prazosin is associated with decrease in nightmare frequency in bulimic patients

The secondary aim of our study is to assess changes in Cortisol levels in bulimic patients with PTSD before and after treatment with prazosin.

Hypothesis 2:

Prazosin use is associated with a decrease of cortisol levels.

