1.3 Secondary Study Endpoints

Secondary Outcome measures: Decrease in total CAPS score, depressed mood, bulimia symptoms and self-harm thoughts on depression scale

AIMS FOR PHASE B:

Phase B will involve using objective polysomnogram measurements (hypothesis 3) in addition to the subjective instruments used in phase A.

The Primary aim of our study is to evaluate the effectiveness of prazosin in bulimic patients experiencing distressing nightmares secondary to PTSD using subjective measures.

Hypothesis 1:

Prazosin is associated with decrease in nightmare frequency in bulimic patients

The secondary aim of our study is to assess changes in Cortisol levels in bulimic patients with PTSD before and after treatment with prazosin

Hypothesis 2:

Prazosin use is associated with a decrease of cortisol levels.

Hypothesis 3:

Prazosin is associated with decrease in REM density & normalization of REM disruption (objective).

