2.3 Study Rationale

To our knowledge, there is no treatment trial for prazosin use in patients with bulimia nervosa struggling with nightmares, looking at either objective or subjective measures. We plan to probe the effectiveness of prazosin in bulimic patients experiencing nightmares due to PTSD using both subjective and objective measures in order to improve future clinical care. The effects of

prazosin on decreasing nightmares and bulimic symptoms on subjective scales and effects on sleep architecture using objective polysomnogram measurements will help inform targeted psychopharmacologic and psychotherapeutic strategies to improve clinical care of bulimic patients struggling with distressing dreams secondary to PTSD. This study will be performed in two phases. Phase A will involve eight participants who will be tested using subjective scales (mentioned below). If Phase A data analysis leads to detection of a signal of efficacy 2 more participants will be recruited to participate in phase B of this trial using objective polysomnogram measurements. The results from this project will aid in establishing a fully powered clinical trial for treatment of nightmares in bulimic patients and improve outcomes in this high risk population.

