Objective Measure: PSG (Polysomnogram) will be conducted at baseline for 3 consecutive nights and the last 3 nights of each treatment arm for a total of 9 nights/ person during Phase B of the study. 2 participants will be enrolled in this phase. All other procedures will be the same as described under Phase A.

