9.2 Statistical methods

Statistical methods

The initial analyses of the data will include univariate exploration of all variables, using histograms, statistical summaries, and other graphical techniques. Expected ranges for all of the variables will be defined a priori, and out of range values, or values identified as outliers will be checked for errors, including going back to the original data forms. In addition to data cleaning, this initial analysis will serve the purpose of describing the patients' characteristics.

Our main objective is to identify the treatment effect. We hypothesize that there will be a reduction in cortisol levels and other subjective scores after being treated with Prazosin, whereas no significant change after being administered with placebo. To examine the treatment effect, both univariate and multivariable methods will be used. The analytic plan for hypothesis 1 and 2 will be similar, except the outcome measurements.

Univariate: T-tests will be used to analysis the mean difference of nightmare score, cortisol level, and other subjective scores.

Multivariable regression model: The mixed effects model will be used to examine the differences of the objective measures and subjective scores between two treatment arms. In these models, we will account for the period effect (period 1 or 2) and sequence effect (sequence Placebo-Prazosin or Prazosin-Placebo). The sequence effect will be treated as a random effect. Demographic characteristics and baseline measures will be treated as confounders and adjusted in the models as well. We expect no significant differences in the outcome variables will be observed between baseline and placebo. Therefore, the analysis will focus on the Prazosin vs. Placebo. Least squares mean, standard error of the mean, and p value for the differences will be presented as the final results.

Statistical Plan (Phase B)

Protocol B is only a feasibility study using 2 subjects therefore statistical support is not required.

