16.0 Number of Subjects

Subjects: 15 patients will be identified and screened for participation in the study. Only 10 patients with Bulimia nervosa and PTSD will complete the study and be included in the final analysis. The additional 5 participants will allow for screen failures or participant withdrawal after consent is obtained. This sample size has been derived from the previous studies in PTSD that have investigated the role of Prazosin in alleviating nightmares and other PTSD symptoms.

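### The Phase A power statement uses 10 patients, but Phase A has 8 (base-case power 68%, not 80%), and the plan does not settle whether Hypothesis 1 is tested on 8 or 10

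*Combined protocol and SAP*

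**What the plan says.** Section 9.0 is titled as the Phase A statistical plan. Within it, section 9.1 gives the power for the CAPS distressing-dream item: "With a sample size of 10 patients, we will have 80% power to detect the treatment effect, at 2-sided alpha level of 0.05". Five further scenarios are tabulated at the same sample size. Section 9.1 also says that power is shown for Hypotheses 1 and 2, but the text and table cover only the nightmare score.

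On the size of Phase A, section 2.3 says: "Phase A will involve eight participants who will be tested using subjective scales". On the rest: "If Phase A data analysis leads to detection of a signal of efficacy 2 more participants will be recruited to participate in phase B". Section 1.1 gives the same 8 and 2 and the same condition. No section gives the signal an endpoint, threshold or test.

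On who is analysed, the documents point two ways.

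- **Towards 10.** Section 16.0: "Only 10 patients with Bulimia nervosa and PTSD will complete the study and be included in the final analysis". The Phase B aims repeat Hypotheses 1 and 2 and say: "Phase B will involve using objective polysomnogram measurements (hypothesis 3) in addition to the subjective instruments used in phase A". The Phase B procedures in section 7 add: "All other procedures will be the same as described under Phase A".
- **Towards 8.** Section 9.2: "Protocol B is only a feasibility study using 2 subjects therefore statistical support is not required".

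**The concern.** The power claim is attached to a phase that has 8 patients, and the 2 who would make it 10 may never be enrolled. A reader cannot tell from section 9.1 what chance the plan gives the Hypothesis 1 test.

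The analysis set matters as much. The Phase A analysis has to be run before Phase B can open, so the 8-patient result is known before any 10-patient analysis exists. With neither set fixed in advance, both results can be seen before one is called the test of Hypothesis 1. The rule that opens Phase B is also undefined, although the project uses it as its go/no-go decision on the way to external funding and a fully powered trial.

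**Working it through.** **Inputs, all from section 9.1.** Base case: placebo mean 6.0 (SD 1.5), prazosin mean 3.5 (SD 2.5), within-patient correlation 0.3, two-sided alpha 0.05, no carry-over. The alternative rows change the means or use correlation 0.4. The design is a two-period crossover (section 7.1), and section 9.2 names t-tests on the mean difference.

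**Formula.** SD of the paired difference = √(1.5² + 2.5² − 2ρ × 1.5 × 2.5). This is √(8.5 − 2.25) = 2.500 for ρ = 0.3 and √(8.5 − 3.0) = 2.345 for ρ = 0.4. Power comes from the noncentral t distribution with df = n − 1 and noncentrality = difference × √n / SD.

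**Base case.**

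- n = 10: noncentrality = 2.5 × √10 / 2.5 = 3.162, df 9, power 80.3%. The stated 80% reproduces.
- n = 8: noncentrality = 2.5 × √8 / 2.5 = 2.828, df 7, power 68.1%.

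**All six rows.**

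| Placebo, prazosin means | ρ | Stated | n = 10 | n = 8 |
|---|---|---|---|---|
| 6.0, 3.5 | 0.3 | 80% | 80.3% | 68.1% |
| 6.0, 3.5 | 0.4 | 85% | 85.0% | 73.5% |
| 6.5, 3.5 | 0.3 | 92% | 92.0% | 82.8% |
| 6.5, 3.5 | 0.4 | 95% | 94.8% | 87.2% |
| 6.5, 4.0 | 0.3 | 81% | 80.3% | 68.1% |
| 6.5, 4.0 | 0.4 | 85% | 85.0% | 73.5% |

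Every stated figure reproduces within 1 point at n = 10, so the method is identified. A normal approximation would give 88.5% at n = 10 and is not what was used. At n = 8, four of the six rows fall below 80%. Adding a period term (df = 6) lowers the base case to 65.7%. That is still not the full section 9.2 model, which also adjusts for demographics and baseline.

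**If the 2 Phase B patients are pooled.** The result depends on the gate, and the documents define none. The four gates below are therefore assumptions; the first three are two-sided p-values from the Phase A test, with the effect in the favourable direction. Each result uses 1,000,000 simulated trials of 10 paired differences with SD 2.5, the first 8 being Phase A. The true difference is 2.5, except in the last row, where it is 0.

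| | p<0.05 | p<0.10 | p<0.20 | Direction only |
|---|---|---|---|---|
| Gate passed | 68% | 82% | 91% | 99.8% |
| Gate passed and pooled p<0.05 | 66% | 76% | 80% | 80% |
| Mean pooled estimate given a signal | 2.81 | 2.71 | 2.61 | 2.51 |
| Significant at 8, not at 10 | 2.2% | 2.2% | 2.2% | 2.2% |
| Significant at 10, not at 8 | 0% | 10.4% | 14.3% | 14.4% |
| No effect: either test favourably significant | 2.5% | 3.2% | 3.6% | 3.6% |

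Rows four and five count trials in which Phase B opened. Their sum is the share in which the two tests disagree: 2, 13, 17 and 17%. The nominal value for the last row is 2.5%.

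**Cortisol.** Section 9.1 gives no mean or SD for Hypothesis 2. With the same test, 80% power needs a standardised paired difference of about 1.16 at n = 8 or 1.00 at n = 10.

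**The case against.** The strongest reply is that section 9.1 powers the whole trial and only its heading is too narrow. Sections 1.1, 9.1 and 16.0 all speak of 10 patients, and for 10 the arithmetic is right. This is a fair reading of intent, and it means that the fault is an inconsistency between sections rather than a miscalculation. It does not rescue the figure as written. Sections 1.1 and 2.3 make the last 2 patients conditional, section 16.0 counts on them unconditionally, and section 9.2 provides no analysis that would include them. Under pooling, the 80% holds with a lenient gate but not with a strict one.

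A second reply is that the pooled results and the error rates rest on gates that appear nowhere in the plan. That is correct, and those figures are illustrations, not bounds. The n = 8 powers do not depend on any gate.

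A third is that the rise to 3.6% needs freedom to report whichever test is favourable. That is also correct. With the pooled test fixed in advance, the favourable false-positive rate is 1.3 to 2.5% over the four gates, so it does not exceed nominal. The inflation is modest and disappears once the set is named.

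Last, this is preparatory work and need not have 80% power. Agreed, and no larger sample is asked for. But the plan itself claims 80%, tests at two-sided 0.05 and presents p-values as final results, so the claim should match the patients tested.

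**Conclusion.** The concern holds. For the 8-patient Phase A test, base-case power is 68%, with a range of 68 to 87% over the plan's own scenarios, against the stated 80 to 95%. These figures use the plan's inputs and its evident method and assume that all 8 complete; with 7 completers the base case is about 60%.

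Whether Hypothesis 1 is tested on 8 or 10 patients is left in conflict between sections 9.2 and 16.0, and the gate between the phases is undefined. For a pooled test, the stated 80% is supported only if that gate is lenient. The claim to show power for Hypothesis 2 is unsupported. Because the primary power statement, the go/no-go rule and the primary analysis set are all affected, this should be corrected before any data are seen.

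**What to change.** 1. **Define the efficacy signal** in sections 1.1 and 2.3 by endpoint, test and numerical threshold.
2. **Name the Hypothesis 1 analysis set before any data are seen**, and make the other sections agree.
   - *If 8:* say in section 16.0 that 8 patients enter the Hypothesis 1 test and that the 2 Phase B patients are only described. Label Hypotheses 1 and 2 as descriptive in the Phase B aims.
   - *If 10:* amend the Phase B sentence in section 9.2 to provide for the pooled analysis. Say in section 16.0 that the final analysis has 10 patients if Phase B opens and 8 otherwise. Give the power under the defined gate, and note that the pooled estimate after a signal is biased upward (2.51 to 2.81 against a true 2.5 under the gates assumed here).
3. **Restate the power sentence and table in section 9.1 for n = 8**, labelled as the power of the Phase A test (base case 68%, range 68 to 87%). This is needed under either choice, because the Phase A analysis is run on 8. If 10 is chosen, show the pooled power beside it.
4. **Remove Hypothesis 2 from the power statement**, or give the detectable standardised cortisol difference (1.16 at n = 8, 1.00 at n = 10).

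The cost is wording in sections 1.1, 2.3, 9.1, 9.2 and 16.0, plus the Phase B aims if 8 is chosen. No patients or visits are added. The stated power becomes less favourable for the Phase A test, and for a pooled test with a strict gate.

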9.2 Statistical methods

Statistical methods

The initial analyses of the data will include univariate exploration of all variables, using histograms, statistical summaries, and other graphical techniques. Expected ranges for all of the variables will be defined a priori, and out of range values, or values identified as outliers will be checked for errors, including going back to the original data forms. In addition to data cleaning, this initial analysis will serve the purpose of describing the patients' characteristics.

Our main objective is to identify the treatment effect. We hypothesize that there will be a reduction in cortisol levels and other subjective scores after being treated with Prazosin, whereas no significant change after being administered with placebo. To examine the treatment effect, both univariate and multivariable methods will be used. The analytic plan for hypothesis 1 and 2 will be similar, except the outcome measurements.

Univariate: T-tests will be used to analysis the mean difference of nightmare score, cortisol level, and other subjective scores.

Multivariable regression model: The mixed effects model will be used to examine the differences of the objective measures and subjective scores between two treatment arms. In these models, we will account for the period effect (period 1 or 2) and sequence effect (sequence Placebo-Prazosin or Prazosin-Placebo). The sequence effect will be treated as a random effect. Demographic characteristics and baseline measures will be treated as confounders and adjusted in the models as well. We expect no significant differences in the outcome variables will be observed between baseline and placebo. Therefore, the analysis will focus on the Prazosin vs. Placebo. Least squares mean, standard error of the mean, and p value for the differences will be presented as the final results.

Statistical Plan (Phase B)

Protocol B is only a feasibility study using 2 subjects therefore statistical support is not required.

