6.3 Waiver or alteration of authorization statements of agreement

7.0 Study Design and Procedures

7.1 Study Design

Study Design: We plan to conduct a 7 week prospective, double blind, placebo controlled crossover study. Each patient, in a randomized design will receive three weeks of prazosin and three weeks of placebo separated by 1 week washout period. A 1-week washout period is considered sufficient, given that the half-life of prazosin is 2-3 hours, and previous studies have demonstrated that the clinical effects of prazosin are eliminated within a week^{10, 11}. The subjects

will be blinded and the randomization list will be sent directly to the research pharmacy. Methylcellulose will be used as placebo.

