7.2.3 Weekly Visits

Symptoms will be reassessed and medication will be adjusted by 1-2 mg increments every 7 days based on clinical response and severity of night mares, to achieve maximum therapeutic benefit while monitoring adverse effects using side effects scale on weekly basis (psychiatrist will be using the scale at every visit). A phone contact by RA will be made on the morning after dose initiation and after each increment to monitor adverse events. The end point for capping the Prazosin dose will be 6 mg daily. The psychiatrist will administer adverse events rating scale and nightmare assessment using Sleep-50 Questionnaire at every psychopharmacologic

visit after initiation of medication in addition to the initial visit. Vital signs will be checked at each visit as well. The participants will have a total of 7 visits with the psychiatrist (1 for initial evaluation and 3 for the dose titration during each study arm). Research pharmacy and RA will determine and track the sequence and random allocation of the medication to ensure blind randomized trial. RA will also gather salivary samples from the patient at end of each study arm (5 diurnal samples for each arm) After 3 weeks on one treatment arm, a wash out period of 1 week will be given prior to starting the second study arm. The same sequence will be repeated for the second study arm and study questionnaires will be repeated on the last day of the washout period. Blood work will be drawn thrice, once at baseline and once at the end of each study arm. 5 Diurnal salivary samples will be collected thrice, once at baseline and once at the end of each study arm. All sets of cortisol level will be collected at the same time points as the baseline level to allow accurate comparisons. All Rating scales will be completed 4 times, once at baseline, once at end of wash out period and once at the end of each study arm. At the end of each study arm, any unused medication will be collected from the participant. Upon completion of the study, participants may want to continue taking the study medication if they experienced positive results. The PI will discuss with each participant if it is appropriate to continue taking the medication.

Study Procedures (PHASE B)

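### Section 9.2 makes the two-level sequence factor the random effect and names no patient effect, so the model as written does not use the within-patient pairing that the crossover and the power table rely on

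*Combined protocol and SAP*

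**What the plan says.** - **Design (section 7.1):** "Each patient, in a randomized design will receive three weeks of prazosin and three weeks of placebo separated by 1 week washout period". Every patient therefore contributes one score under each treatment.
- **Power (section 9.1):** "We assumed that the correlation between two scores for the same patient equals to 0.3". A value of 0.4 is used in the alternative rows of the table.
- **Model (section 9.2):** a mixed effects model compares the two treatments and accounts for period and sequence, and "The sequence effect will be treated as a random effect". Covariates are added: "Demographic characteristics and baseline measures will be treated as confounders and adjusted in the models as well". The least squares means, standard errors and p-values from this model are the stated final results.
- **Univariate analysis (section 9.2):** "T-tests will be used to analysis the mean difference of nightmare score, cortisol level, and other subjective scores". Whether these tests are paired is not stated.

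Neither document section mentions a patient effect, a repeated-measures covariance or a within-patient error term.

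**The concern.** Sequence has two levels, and each level contains both treatments and both periods. A sequence term, fixed or random, therefore cannot separate one patient from another within a sequence. If it is the only random effect, each patient's two scores enter the model as independent residuals. Differences between patients then stay in the error term, although a crossover is designed to remove them from the treatment comparison. A variance estimated from two groups is also poorly determined.

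The standard error and p-value are at stake. With equal sequences and complete pairs the treatment estimate itself is unaffected in the model without covariates. With about ten patients, a miscalibrated standard error can change what the trial reports. Two analysts who follow section 9.2, one literally and one supplying the usual patient term, would give different p-values from the same data.

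**Working it through.** **Inputs, all from section 9.1.** Placebo SD 1.5; prazosin SD 2.5; mean difference 2.5 (6.0 − 3.5 or 6.5 − 4.0) or 3.0 (6.5 − 3.5); correlation ρ = 0.3 or 0.4; n = 10; two-sided alpha 0.05.

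**Step 1: reproduce the power table.** SD of the within-patient difference = √(1.5² + 2.5² − 2ρ·1.5·2.5) = √(8.5 − 7.5ρ), which is 2.500 at ρ = 0.3 and 2.345 at ρ = 0.4. Power comes from the noncentral t distribution with 9 df and noncentrality difference/(SD/√10). The last column is the two-sample formula with zero correlation and 18 df.

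| Placebo / prazosin | ρ | Stated | Paired t | Unpaired, zero correlation |
|---|---|---|---|---|
| 6.0 / 3.5 | 0.3 | 80% | 80.3% | 72.7% |
| 6.0 / 3.5 | 0.4 | 85% | 85.0% | 72.7% |
| 6.5 / 3.5 | 0.3 | 92% | 92.0% | 86.8% |
| 6.5 / 3.5 | 0.4 | 95% | 94.8% | 86.8% |
| 6.5 / 4.0 | 0.3 | 81% | 80.3% | 72.7% |
| 6.5 / 4.0 | 0.4 | 85% | 85.0% | 72.7% |

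The paired test matches every row to within 1 point. An unpaired t-test applied to correlated scores gives 75–76% (difference 2.5) or 90–91% (difference 3.0). It gains only about 1 point when ρ goes from 0.3 to 0.4, whereas the stated figures gain 3 to 5. The trial was sized on pairing.

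**Step 2: standard error without baseline adjustment.**
- As written: about √((1.5² + 2.5²)/10) = √0.85 = 0.92.
- True: 2.500/√10 = 0.79 (ρ = 0.3) or 2.345/√10 = 0.74 (ρ = 0.4).
- Ratio: √(8.5/(8.5 − 7.5ρ)) = 1.17 or 1.24, so 17% or 24% too large.

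**Step 3: type I error and power without baseline adjustment.** Simulation of 40,000 crossovers per cell, 5 patients per sequence, normal scores. The model has treatment and period and no patient term, with the sequence variance at its two extremes (zero, or sequence fully fitted). The difference is 2.5 for power.

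| | ρ = 0.3 | ρ = 0.4 |
|---|---|---|
| Mean SE as written | 0.90–0.91 | 0.90–0.91 |
| Type I error as written | 2.6–2.8% | 2.0–2.1% |
| Power as written | 74–75% | 75–76% |
| Type I error, within-patient analysis | 5.0% | 4.8% |
| Power, within-patient analysis | 79% | 84% |

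REML fits at ρ = 0.3 (300 data sets) agree: mean SE 0.89 with a random intercept for sequence only, 0.74 with one for patient.

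**Step 4: one baseline value per patient.** The documents give no correlation between baseline and endpoint, so r, taken as the same with each score, is assumed to be 0.3 to 0.6. The correlation of the two scores given baseline is (ρ − r²)/(1 − r²):

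| r | ρ = 0.3 | ρ = 0.4 |
|---|---|---|
| 0.3 | 0.23 | 0.34 |
| 0.4 | 0.17 | 0.29 |
| 0.5 | 0.07 | 0.20 |
| 0.6 | −0.09 | 0.06 |

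Where this correlation is non-negative, simulated type I error as written runs from about 2.5% to about nominal. It clearly exceeds 5% only in the negative cell (r = 0.6, ρ = 0.3), at up to 6.4%. Across all cells, power as written is 77–87% against 80–84% with a patient effect (ρ = 0.3), and 79–88% against 84–86% (ρ = 0.4).

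**The case against.** **Silence is not exclusion.** Section 9.2 does not call sequence the only random effect. It specifies a mixed effects model for a crossover, and section 9.1 assumes within-patient correlation. A reader might infer that the authors chose to ignore pairing; the documents do not support that, and their own power table points the other way. What stands is that the one sentence naming a random effect names sequence, and an analyst who follows it gets the wrong error term.

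**The no-baseline figures belong to a model that the plan does not specify.** This is right. Section 9.2 adjusts for baseline and demographics, so Steps 2 and 3 are a bound and not the expected loss. Demographic covariates were not simulated.

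**A reader might infer a false-positive problem.** The documents do not support this. At the plan's positive correlations the error is conservative without baseline adjustment. With a single baseline, it is clearly liberal only if a patient's two scores are negatively correlated once baseline is known, and nothing in the documents suggests that.

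**Baseline adjustment might do the work of a patient effect.** It can do part of it, but how much cannot be determined from the documents. Section 9.1 treats baseline as a constant ("we assume the baseline nightmare score equals to 6.5, regardless of the treatment period"). Rating scales have two possible baselines ("All Rating scales will be completed 4 times, once at baseline, once at end of wash out period"), while cortisol has one ("5 Diurnal salivary samples will be collected thrice, once at baseline and once at the end of each study arm"). Step 4 covers only the single-baseline case.

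**Conclusion.** The concern holds as a defect in the specified model: if section 9.2 is followed literally, the standard error and p-value do not use the pairing on which the trial was designed and sized. Without baseline adjustment the cost at n = 10 is a standard error 17% or 24% too large, and about 4 to 5 points of power at ρ = 0.3 or 8 to 9 points at ρ = 0.4. This is an upper guide to the loss. With a single baseline the loss is smaller and may vanish, and the power ranges with and without a patient effect overlap.

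Confidence is high that the patient term is not written down, and lower on the size of the consequence. The figures assume the SDs and correlations of section 9.1, normal scores, five patients per sequence and complete pairs. Section 24.1.3 does not guarantee equal sequences, and section 16.0 allows for withdrawals. The baseline correlations are assumptions.

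This should be fixed before the data are analysed. It does not call the design or the section 9.1 power calculation into question.

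**What to change.** In section 9.2:
1. Replace the sentence on the sequence effect with: *Patient (within sequence) will be a random effect; treatment, period and sequence will be fixed effects.*
2. Name a small-sample degrees-of-freedom method, for example Kenward-Roger. With ten patients this choice affects the p-value.
3. State that the t-tests comparing prazosin with placebo are paired within patient.

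The cost is two or three sentences of SAP wording, with no change to the design, the visits or the data collected. If a patient effect was always intended, the change simply records it.
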